6.6.2 Triplet cohort

If ≥ 2 of the first 3 patients or of the 6 patients treated at the initial DL present with DLTs, the SC may decide to decrease the dose of tusamitamab rfvantsine to DL -1 (120 mg/m² in combination with 10 mg/kg ramucirumab). The tolerability of the reduced DL will be assessed in at least 6 participants. Dose reduction in the case of 2 or more DLTs for the cohort is shown in [Table 10](#).

Table 10 - Dose reduction for triplet cohort

Dose level (DL)	tusamitamab rfvantsine	ramucirumab	pembrolizumab
Starting dose	150 mg/m ² Q3W	10 mg/kg Q3W	200 mg Q3W
Minus -1 (DL-1)	120 mg/m ² Q3W	10 mg/kg Q3W	200 mg Q3W

DL=dose level; Q3W=every 3 weeks.

Infusion of tusamitamab rfvantsine will be administered at least 1 hour after the end of ramucirumab infusion. For patients with a BSA >2.20 m², the tusamitamab rfvantsine dose will be calculated based on a BSA of 2.20 m².

6.6.3 Doublet cohort (Part 1 and Part 2) and triplet cohort: Requirements for retreatment

For the retreatment of patients on Day 1 of each subsequent cycle, the following conditions should be met:

- Neutrophils count $\geq 1.5 \times 10^9/L$.
- Platelets $\geq 100 \times 10^9/L$.
- Total bilirubin $\leq 1.5 \times ULN$.
- AST, ALT $\leq 2.5 \times ULN$ or $\leq 5 \times ULN$ in case of documented liver metastasis.
- No IMP-related toxicity Grade >1 (except for alopecia) or baseline severity.
- Urine protein:
 - $<2+$ on dipstick or urinalysis for C1D1,
 - $\leq 2+$ on dipstick or urinalysis for subsequent infusions,
 - OR
 - <2 g on 24 hours urine collection.
- Hypertension is controlled, every attempt should be made to control blood pressure (<140 mmHg systolic and <90 mmHg diastolic).
- Wound healing: any wound is fully healed.

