	Grade 3-4 Severe Eg, symptomatic bronchospasm, urticaria lesions covering $>30\%$ BSA, hypotension, angioedema.	Interrupt ramucirumab infusion and prematurely definitively discontinue ramucirumab	Interrupt tusamitamab rvtansine infusion and prematurely discontinue tusamitamab rvtansine and consider infusion delay.	Give diphenhydramine 50 mg IV and/or dexamethasone 10 mg IV and/or epinephrine and any required treatment per investigator judgement.
Ocular toxicity: Keratopathy/keratitis ^b associated with tusamitamab rvtansine	Grade 1 - Asymptomatic Corneal lesions only observed on routine ocular examination and not requiring topical treatment.	Administer ramucirumab at same dose, and same day as tusamitamab rvtansine	Next infusion of tusamitamab rvtansine at the same dose, with or without cycle delay, depending on the recommendation from the ophthalmologist (nature and extent of the lesion).	Standard ocular examination is planned as recommended by the ophthalmologist.
	Grade 2 Symptomatic or requiring topical treatment (curative) or limiting instrumental activity of daily life. Moderate decrease in visual acuity (best corrected visual acuity 20/40 and better or 3 lines or less decreased vision from known baseline)	Administer ramucirumab as planned, and re-introduce tusamitamab rvtansine when recovery to Grade 1	1 st episode: Omit tusamitamab rvtansine until resolution to Grade 1 (asymptomatic) and restart tusamitamab rvtansine at the same dose. 2 nd episode: Omit SAR until resolution to Grade 1 (asymptomatic) and tusamitamab rvtansine dose reduction. 3 rd episode: depending on benefit risk, premature definitive discontinuation of tusamitamab rvtansine may be envisaged	Standard ocular examination weekly until resolution ^{c, d} . Start curative treatment per ophthalmologist recommendation. After resuming study treatment, participant should be followed with standard ocular examination by every 2 cycles, even asymptomatic during next 4 cycles. If no recurrence, standard process with follow-up with ocular symptom is resumed. Management of study drug upon recurrence to be discussed according to Grade of the event at recurrence, clinical benefit from study drug and recommendation from the ophthalmologist.

Event	Symptoms severity (Nadir) (NCI CTCAE v5)	Management of IMP dosing (ramucirumab))	Management of IMP dosing (tusamitamab rvtansine)	Supportive care guidelines

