	Grade 3 Symptomatic with marked decrease in visual acuity (best corrected visual acuity worse than 20/40 or more than 3 lines of decreased vision from known baseline, up to 20/200); corneal ulcer; limiting selfcare activity of daily life	Administer ramucirumab as planned, and re-introduce tusamitamab rvtansine when recovery to Grade 1	1 st episode: Omit tusamitamab rvtansine until resolution (asymptomatic) and restart tusamitamab rvtansine with dose reduction. 2 nd episode: definitive discontinuation of tusamitamab rvtansine.	Standard ocular examination weekly until resolution ^{c, d} . Start curative treatment per ophthalmologist recommendation. After resuming study treatment, participant should be followed with standard ocular examination by every 2 cycles, even asymptomatic during next four cycles. If no recurrence, standard process with follow-up with ocular symptom is resumed Management of study drug upon recurrence to be discussed according to Grade of the event at recurrence, clinical benefit from study drug and recommendation from the ophthalmologist
	Grade 4 Perforation or best corrected visual acuity of 20/200 or worse in the affected eye.	Administer ramucirumab as planned,	Definitive discontinuation of tusamitamab rvtansine.	Complete the corneal examination as recommended by ophthalmologist. Repeat the standard ocular examination weekly ^c until resolution ^d . Start curative treatment per ophthalmologist recommendation.
Conduction disorder associated with tusamitamab rvtansine	Grade 1 Mild symptoms	Administer ramucirumab as planned,	tusamitamab rvtansine administration to be continued upon decision by the Investigator and Sponsor, depending on the nature of the conduction disorder.	ECG performed once weekly until event resolution. Additional evaluations such as LVEF and Holter monitoring should be performed when relevant.
	Grade ≥2	Administer ramucirumab as planned,	Definitive discontinuation of tusamitamab rvtansine.	ECG to be repeated twice weekly until event resolution. Prompt cardiology consultation Additional evaluations such LVEF and Holter monitoring should be performed when relevant.

Event	Symptoms severity (Nadir) (NCI CTCAE v5)	Management of IMP dosing (ramucirumab)	Management of IMP dosing (tusamitamab rfvansine)	Supportive care guidelines

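### The Grade 3 keratopathy row of Protocol Appendix 4 gives two conflicting instructions for a second Grade 3 episode: mandatory discontinuation of tusamitamab ravtansine, and case-by-case discussion

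*Protocol*

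**What the plan says.** The ocular toxicity part of the table in Protocol Section 10.4 (Appendix 4) has one column for ramucirumab dosing, one for tusamitamab dosing and one for supportive care. In the Grade 3 row:

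- **Tusamitamab column, first episode:** "Omit tusamitamab rvtansine until resolution (asymptomatic) and restart tusamitamab rvtansine with dose reduction".
- **Tusamitamab column, second episode:** "2 nd episode: definitive discontinuation of tusamitamab rvtansine". No exception is stated.
- **Ramucirumab column:** "Administer ramucirumab as planned, and re-introduce tusamitamab rvtansine when recovery to Grade 1".
- **Supportive-care column:** "Management of study drug upon recurrence to be discussed according to Grade of the event at recurrence, clinical benefit from study drug", followed by the ophthalmologist's recommendation. No exception is made for a second Grade 3 event.

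The Grade 2 row carries the same discussion sentence. Its tusamitamab column makes discontinuation at a third episode discretionary, and its first-episode restart rule is "Omit tusamitamab rvtansine until resolution to Grade 1 (asymptomatic) and restart tusamitamab rvtansine at the same dose". The Grade 4 row mandates discontinuation and has no discussion sentence.

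**The concern.** Corneal toxicity is the main anticipated risk (Protocol Section 2.3), and the dose-limiting toxicities in the first-in-human study were mainly Grade 3 keratopathy (Section 2.1). Grade 3 or higher keratopathy is a DLT (Table 5) and an adverse event of special interest (Section 8.3.1). Sections 6.6.4 and 8.2.6.2.1 send sites to Appendix 4 for dose modification.

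A site that follows the tusamitamab column stops the drug at a second Grade 3 episode. A site that follows the supportive-care column may weigh clinical benefit and could redose a participant who is responding. Two participants with the same sight-affecting event could then be managed differently under the same protocol.

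SAP Section 4.7.2 tabulates corneal events by discontinuation of tusamitamab ravtansine, dose modification, action taken and recurrence. For these participants, those outputs would partly reflect which column the site read.

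**Working it through.** The documents state no figure on this point, so the check is a comparison of texts, followed by one line of arithmetic.

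**1. Which recurrences are in conflict?** The discussion sentence depends on the grade at recurrence.

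- Recurrence below Grade 3: the tusamitamab column of the Grade 3 row counts episodes and does not clearly address a milder one. The discussion sentence can fill that gap, so there is no contradiction.
- Recurrence at Grade 3: one cell is mandatory and the other leaves study drug to discussion. Both cannot be followed as written.

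**2. How do the neighbouring rows treat this?**

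| Row | Mandatory stop of tusamitamab | Discussion sentence |
|---|---|---|
| Grade 2 | No (third episode discretionary) | Yes |
| Grade 3 | Yes (second episode) | Yes |
| Grade 4 | Yes | No |

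Only the Grade 3 row combines the two.

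**3. Does Section 6.6.4 settle it?**

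- The first Grade 3 episode uses the one tusamitamab reduction. Table 11 (doublet) and Table 12 (triplet) do not permit a second, and the text below them requires discontinuation when an event would call for another. This leans the same way as the tusamitamab column.
- The same section says that a second reduction may be needed and is decided case by case with the sponsor. A discussion that ended in continuing at the already reduced dose would not be a further reduction at all.
- Its rule of taking the most conservative adjustment is written for a participant with several adverse reactions, not for two instructions on one event.

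Section 6.6.4 therefore does not settle the point.

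**4. Restart after the first Grade 3 episode.** The ramucirumab column says "re-introduce tusamitamab rvtansine when recovery to Grade 1". The tusamitamab column asks for resolution with asymptomatic in brackets, and lacks the reference to Grade 1 found in the Grade 2 row. The table heads its Grade 1 row as asymptomatic and defines it as "Corneal lesions only observed on routine ocular examination and not requiring topical treatment". Section 6.6.3 sets a general retreatment condition: "No IMP-related toxicity Grade >1 (except for alopecia) or baseline severity". Read together, these allow a single threshold at Grade 1. Section 8.2.6.2 does separate resolution to Grade 1 from total resolution, but for the schedule of eye examinations, not for restart. The finding is inconsistent wording.

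**5. Size.** Inputs: up to approximately 36 treated doublet participants (Protocol Section 9.2); approximately 30 to 36 (SAP Section 1.1).

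- Shift in the corneal discontinuation rate per participant handled differently: 1/36 = 2.8 percentage points.
- At the lower end of the SAP range: 1/30 = 3.3 percentage points.

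**6. Primary endpoints.** DLT incidence counts participants with at least one DLT in Cycles 1 and 2 (SAP Section 4.3.2.1). A participant whose first Grade 3 episode falls in that window is already counted. If the first falls later, so does the second. A second episode therefore adds nothing to the count. For ORR, SAP Section 4.3.2.2 uses tumor assessments regardless of study intervention discontinuation.

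**The case against.** The strongest reply is that the dosing columns govern dosing. The tusamitamab column gives an explicit second-episode action, the other sentence sits under supportive care and repeats the Grade 2 row, and Section 6.6.4 points towards discontinuation. That section also requires sponsor consultation for dose modifications that differ from the protocol, unless immediate safety requires them, so sites are unlikely to redose entirely on their own.

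Much of this stands, and it narrows the point to a repeat Grade 3 event. It does not remove it. The sentence is about study drug, no text ranks the columns, and a site that follows the supportive-care column can hold that it is following the protocol.

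A reader might also infer that the row sets two different restart thresholds, because Grade 1 still has corneal lesions. The documents do not support that as fact. The tusamitamab cell refers to absence of symptoms, not of lesions, and the table uses asymptomatic as its label for Grade 1. A participant without symptoms who still needs topical treatment falls under the table's Grade 2 definition, and Section 6.6.3 already bars retreatment in that case. What remains is wording that should match and does not.

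**Conclusion.** The Grade 3 keratopathy row contradicts itself for a second Grade 3 episode, and Section 6.6.4 does not resolve it. The restart wording is inconsistent, possibly without any difference in meaning. No view is taken here on which rule is right.

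The consequence lies in participant safety and in descriptive corneal outputs for the doublet, at 2.8 percentage points per participant handled differently with 36 treated. The number of such participants is unknown, because the documents give no rate of repeat Grade 3 events. Three larger readings are tempting and are not supported:

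- **A count of those affected.** An assumed Grade 3 rate of 5% to 15% gives 0.05 × 36 = 1.8 to 0.15 × 36 = 5.4 participants. These would be first events at a rate that the documents do not state. Participants with a second Grade 3 event are a subset of unknown size.
- **A shift of 1/6 = 16.7 points in the triplet.** The row applies to that cohort, but SAP Section 1.1 says that the SAP does not cover it, so the corneal outputs cited here are not defined for it. Its planned size is also 6 to 12, not fixed at 6.
- **Bias in a primary endpoint.** The DLT count cannot change through a second episode, ORR is analysed regardless of discontinuation, and the safety analyses are descriptive without testing (SAP Section 4.7).

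**What to change.** Reconcile the Grade 3 row of Appendix 4 across its columns and with Section 6.6.4:

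1. State one action for a second Grade 3 episode, and make the case-by-case sentence on a second reduction in Section 6.6.4 consistent with it.
2. Limit the discussion sentence in the supportive-care column to recurrences which that action does not cover.
3. Use identical restart wording in the ramucirumab and tusamitamab columns.

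The sponsor decides which rule and which threshold apply. The cost is an edit to one table row and a check of one sentence in Section 6.6.4. Sample size and analysis methods do not change.

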6.6.4 Dose adjustment/dose delay

Dose adjustment and/or cycle delay are permitted in case of adverse reaction. In case of toxicity, cycle delays and dose modifications should be implemented according to Appendix 4 ([Section 10.4](#)). Every effort will be made to administer the full dose regimen and maximize dose intensity.

Dose adjustments will be made according to the worst grade of adverse reaction observed within a cycle. If a participant experiences several adverse reactions and there are conflicting recommendations, the most conservative dose adjustment recommended should be followed.

Administration of the study treatment will be discontinued in the event of a TEAE that persists despite appropriate dose modifications or any other AE that, in the opinion of the Investigator, warrants discontinuation.

Pembrolizumab, ramucirumab or tusamitamab rvtansine can be discontinued prematurely. The patient will remain on study treatment until the last IMP can be discontinued until disease progression, unacceptable AE, or the participant's or investigator's decision to stop the treatment. The reason for premature discontinuation will be captured in the appropriate eCRF page.

Dose modifications different from those stated in the protocol should be made only in consultation with the Sponsor unless required for immediate participant safety.

All changes to study treatment administration must be recorded in the eCRF.

In the event of neutropenia, therapeutic G-CSF should be administered according to the current American Society of Clinical Oncology (ASCO) guidelines ([23](#)). In case of neutropenia or febrile neutropenia, prophylactic G-CSF should be started and in case of second episode beside prophylactic G-CSF, then dose should be reduced.

The acceptable treatment window for tusamitamab rvtansine and ramucirumab and pembrolizumab administration is ± 2 days for a Q2W (doublet cohort) and ± 3 days for a Q3W administration (triplet cohort).

See Appendix 4 in [Section 10.4](#) for further guidance in dose modification or discontinuation. Approved product label should be followed for patient receiving ramucirumab treatment for supportive care and dose modification requirement due to not listed adverse events. During the conduct of the study, second dose reduction may be needed, and need to be decided case by case discussion with the sponsor.

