8.2.6.5 Liver function tests

Hepatic enzyme increase has been reported with tusamitamab ravtansine administration as monotherapy or ramucirumab. Patients should be carefully followed and in case of Grade ≥ 3 abnormal liver function tests, additional liver function tests will be done every 2 to 3 days until recovery to baseline value. Tusamitamab ravtansine should be permanently discontinued in case of drug-induced Grade 4 liver enzyme increase. For stopping rules for ramucirumab administration, the current product leaflet should be followed.

Grade ≥ 3 (ie, $> 5 \times$ ULN) increased liver enzyme events should be reported as AESIs.

8.2.6.6 *Hypertension*

An increased incidence of severe hypertension (CTCAE Grade 3) has been reported in patients receiving ramucirumab as compared with placebo. In most cases, hypertension was controlled using standard antihypertensive treatment. Preexisting hypertension should be controlled before starting ramucirumab treatment. Monitoring of blood pressure is required during ramucirumab therapy. Every attempt should be made to control blood pressure to systolic <140 mmHg and diastolic <90 mmHg prior to starting treatment with ramucirumab. Routine clinical and laboratory monitoring is required in patients who again develop hypertension or experience a deterioration in previous hypertension.

Withhold ramucirumab for severe hypertension until medically controlled. Permanently discontinue ramucirumab for medically significant hypertension that cannot be controlled with antihypertensive therapy or in patients with hypertensive crisis or hypertensive encephalopathy.

8.2.6.7 *Proteinuria*

Proteinuria is an adverse effect for all therapies targeting the vascular endothelial growth factor (VEGF)/VEGFR-2 pathway, including ramucirumab. Proteinuria has been associated with ramucirumab in clinical studies; the majority of events were Grade 1 or 2.

Monitor proteinuria by urine dipstick and/or urinary protein creatinine ratio. If the result of the urine dipstick is 2+ or greater, perform a 24 hours urine collection for protein measurement.

Withhold ramucirumab for urine protein levels of 2 or more grams collected over 24 hours. Reinitiate ramucirumab at a reduced dose once the urine protein level returns to less than 2 grams over 24 hours. Permanently discontinue ramucirumab for urine protein levels greater than 3 grams over 24 hours, or in the setting of nephrotic syndrome.

8.2.6.8 *Bleeding/Hemorrhage*

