Event	Symptoms severity (Nadir) (NCI CTCAE v5)	Management of IMP dosing (ramucirumab)	Management of IMP dosing (tusamitamab rfvansine)	Supportive care guidelines
Febrile neutropenia	Grade 3 Absolute neutrophil count <1000/mm ³ with a single temperature of >38.3°C (101°F) or a sustained temperature of ≥38°C (100.4°F) for more than 1 hour	Delay cycle until absolute neutrophil count >1500/mm ³ . 1st episode administer next cycle at the same dose and administer G-CSF 2nd episode: administer ramucirumab at reduce dose 3rd episode: definitive discontinuation	Delay cycle until absolute neutrophil count >1500/mm ³ . 1st episode administer next cycle at the same dose and administer G-CSF 2nd episode: administer tusamitamab rfvansine at reduce dose 3rd episode: definitive discontinuation	To ensure relative dose intensity, G-CSF is recommended as secondary prophylaxis in all patients with Grade 3 febrile neutropenia ASCO guideline is recommended for supportive treatment if there are no defined clinical standards (23)
	Grade 4 Life-threatening consequences	Administration changes to be decided at the Investigator's discretion per product label	Administration changes to be decided at the Investigator's discretion. 1st episode: administer next cycle at reduced dose and administer G-CSF 2nd episode: definitive discontinuation	
Hypertension	Grade 3 Severe hypertension	Withhold ramucirumab until controlled with medical management, and restart at same dose	Administer tusamitamab rfvansine as planned	
	Grade 4 Severe hypertension that cannot be controlled with antihypertensive therapy	Definitively discontinue ramucirumab	Administer tusamitamab rfvansine as planned	
Proteinuria	First occurrence of increased urine protein levels greater than or equal to 2 g per 24 hours	Omit ramucirumab until urine protein level is ≤2 g per 24 hours; then resume ramucirumab at a reduced dose (in doublet cohort, 8 mg at 1st episode, then 5 mg if 2nd episode and in triplet cohort, 8 mg at 1 st episode, then 6 mg if 2d episode)	Administer tusamitamab rfvansine as planned	
	Reoccurrence of urine protein level greater than 2 g per 24 hours following initial dose reduction	Omit ramucirumab until protein level is ≤2 g per 24 hours; then resume ramucirumab at a reduced dose:(6 mg or 5 mg)	Administer tusamitamab rfvansine as planned	

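### Appendix 4's Grade 4 hypertension row names only uncontrollable hypertension as the permanent ramucirumab stop, while Section 8.2.6.6 also stops for hypertensive crisis and hypertensive encephalopathy

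*Protocol*

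**What the plan says.** Section 8.2.6.6 of the protocol says: "Permanently discontinue ramucirumab for medically significant hypertension that cannot be controlled with antihypertensive therapy or in patients with hypertensive crisis or hypertensive encephalopathy". Its preceding sentence has ramucirumab withheld for severe hypertension until it is medically controlled.

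The first table in Section 10.4 (Appendix 4) has two hypertension rows:

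- **Grade 3**, described as severe hypertension. Ramucirumab action: "Withhold ramucirumab until controlled with medical management, and restart at same dose".
- **Grade 4**, described as "Severe hypertension that cannot be controlled with antihypertensive therapy". Ramucirumab action: definitive discontinuation.

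Neither row mentions crisis or encephalopathy.

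Section 6.6.4 gives the table its force: "In case of toxicity, cycle delays and dose modifications should be implemented according to Appendix 4". It adds: "Dose adjustments will be made according to the worst grade of adverse reaction observed within a cycle". Section 8.2.6 introduces its own subsections, 8.2.6.6 among them, as a reminder of the most relevant events. For adverse events specific to ramucirumab it points to the prescribing information.

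**The concern.** The protocol treats crisis and encephalopathy as reasons to stop ramucirumab for good. In Section 8.2.6.6 the qualifier about control attaches only to the first trigger; the other two stand alone. The dosing table keeps the first and leaves out the other two. The short version is in the table that sites are told to follow, and the full version is in text that calls itself a reminder.

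At stake is whether a site working from the table alone can read the stop directly or must infer it from the grade label. If it reads the descriptors instead, a crisis that responds to treatment does not fit the row about hypertension that cannot be controlled, and the nearest remaining row says to restart at the same dose.

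**Working it through.** There is no plan figure to reproduce. The check is a comparison of texts.

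**1. The two rules side by side**

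| Condition | Section 8.2.6.6 | Appendix 4, by row descriptor |
|---|---|---|
| Hypertension that cannot be controlled | Permanent stop | Permanent stop (Grade 4 row) |
| Hypertensive crisis | Permanent stop | Not named |
| Hypertensive encephalopathy | Permanent stop | Not named |
| Severe hypertension, then controlled | Withhold until controlled | Withhold, then restart at same dose (Grade 3 row) |

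Stop triggers in Section 8.2.6.6: 3. Named in the Grade 4 descriptor: 1. Not named: 3 − 1 = 2. Section 8.2.6.6 says medically significant where Appendix 4 says severe; I count these as the same trigger.

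**2. One participant followed through the text.** Suppose a participant has a hypertensive crisis, pressure is controlled, and the event resolves before the next cycle.

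- *By Section 8.2.6.6:* permanent stop.
- *By Appendix 4, using the grade:* the column is headed "Symptoms severity (Nadir) (NCI CTCAE v5" and Section 6.6.4 applies the worst grade in the cycle. If the event was graded 4, the participant enters the stop row even though pressure was later controlled.
- *By Appendix 4, using the descriptor:* the hypertension was controlled, so the Grade 4 wording does not describe it. The Grade 3 row restarts at the same dose.
- *By the Section 6.6.3 retreatment conditions:* "No IMP-related toxicity Grade >1 (except for alopecia) or baseline severity", together with controlled blood pressure. These delay dosing; once they are met they no longer prevent it.

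The third route gives the opposite action from the first. The second agrees with the first only if the site grades the event 4 and lets the grade override the descriptor.

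**3. Does the protocol treat Grade 4 and uncontrollable as the same thing?** Table 5 in Section 4.1 lists Grade 4 hypertension and refractory hypertension as alternatives, so there it does not. In Appendix 4 the row descriptor equates them.

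**4. Do descriptors matter elsewhere in the table?** Yes. Grade 4 neutropenia has different actions depending on whether it lasts more than 7 days.

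**5. Omission or deliberate shortening?** The neighbouring ramucirumab stop rules carry over whole. Proteinuria above 3 g per 24 hours, or nephrotic syndrome, appears in both Section 8.2.6.7 and Appendix 4. Grade 3 or 4 hemorrhage (8.2.6.8) and any arterial thromboembolic event (8.2.6.9) also match. Across 8.2.6.6 to 8.2.6.9, hypertension is the only rule that loses triggers. The nephrotic syndrome entry shows that the table does name a clinical syndrome when it is a stop trigger. This points to an omission.

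**6. Does any text settle which rule prevails?** I found none that clearly does. The most-conservative rule in Section 6.6.4 is worded for several concurrent reactions, not for two sections that differ on one reaction. The product-label fallback there is for events not listed, and hypertension is listed.

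**The case against.** The strongest reply is that nothing is missing from the protocol. Section 8.2.6.6 is binding and complete, and a shorter table cell does not repeal it. To reach the restart row by grade, a site would have to call a crisis or encephalopathy Grade 3, and no text says to do so. The same table describes Grade 4 as life-threatening for febrile neutropenia and neuropathy. If Table 5 separates Grade 4 from refractory hypertension, then Grade 4 can include events that were controlled, and the Grade 4 label catches them.

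There are further safeguards. Encephalopathy is arguably an unlisted event, in which case the product label governs. The investigator may stop treatment for any adverse event judged to warrant it. On departures from the protocol, Section 6.6.4 says: "Dose modifications different from those stated in the protocol should be made only in consultation with the Sponsor". In the DLT window, Grade 4 or refractory hypertension is a DLT unless due to progression or an obviously unrelated cause, and protocol-defined DLTs are adverse events of special interest, reported to the sponsor within 24 hours.

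Most of this stands, and it is why re-exposure is unlikely. It does not remove the difference between the two rules. The grade argument depends on the CTCAE v5 definition, which the documents do not reproduce. The consultation rule covers departures from the protocol, and a site following the table literally may believe it is complying. Classifying an event as a DLT guides the dose level of tusamitamab ravtansine; it does not state what happens to that participant's ramucirumab.

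A reader might infer more: that the protocol directs re-exposure after a crisis, or that participants are likely to be harmed. The documents do not support either. No row says ramucirumab may restart after crisis or encephalopathy, Section 8.2.6.6 says the contrary, and no event rate is given.

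**Conclusion.** The point holds as an internal inconsistency in a safety stopping rule, and it is minor. The operative dosing table names one of the protocol's three permanent-stop triggers for hypertension, and its descriptors could be read to permit a restart after a controlled crisis or encephalopathy. I judge that outcome possible but unlikely.

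This rests on two assumptions: that the *or* in Section 8.2.6.6 makes crisis and encephalopathy stops in their own right, which is its plain sense, and that some sites will read the row descriptor as limiting the row. If every such event is graded 4 and sites act on the grade alone, the two texts give the same action and only the wording differs.

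The documents give no basis for a number of affected participants, so none is offered. The inconsistency does not alter the objective response rate analysis, the DLT definition, the estimands or any other SAP analysis.

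**What to change.** Extend the descriptor of the Appendix 4 Grade 4 hypertension row. Keep "Severe hypertension that cannot be controlled with antihypertensive therapy" and add: *or hypertensive crisis or hypertensive encephalopathy (whether or not later controlled)*. The ramucirumab action stays as definitive discontinuation.

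The words in parentheses are not in Section 8.2.6.6. They spell out what its structure already implies and close the descriptor reading; the same words could be added to 8.2.6.6 so that the two texts match exactly.

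The cost is one phrase in one table row, which can go into the next amendment. It needs no new data collection, no change to Table 5 and no change to the SAP.
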